In addition to the above considerations, this intervention targets the role of patient facing technologies in health information sharing. The availability of both patient and provider-facing technologies to improve health information exchange is rapidly evolving. The My HealtheVet Program Office anticipates that veterans will be able to send their CCD electronically directly from the MyHealtheVet website as of Fall/Winter 2014. In addition, [name] is working with local and national initiatives to promote provider-to-provider and state-based health information exchanges where the patient is not the intermediary. Though exciting, these technical developments are not currently available so they could not be incorporated into the design of this study. However, if they do become available during the study, the team and the Executive Committee will explore whether or not it would make sense to revise study methods to include them. The main focus of the assessments within the study is not whether a specific technology is used, but whether there is accurate and timely communication. At this level of analysis, we may be able to change the specific technology used, yet still determine the impact of health information sharing on the quality and efficiency of care provided.

Sample: Sixty dual use veterans who have a non-VA provider and who are not already using My HealtheVet for health information sharing will be recruited from the Iowa City VA Health Care System. Based on earlier research that identified criteria for optimal impact of CC(15-17), participants must have at least one of the following chronic illnesses or ambulatory care sensitive conditions: diabetes, chronic obstructive pulmonary disease, hypertension, congestive heart failure, angina, asthma, coronary artery disease, arthritis, gynecologic conditions, or cancer -as determined by medical record review. We will oversample women veterans so that the final sample contains at least 20 women veterans -30% of the total sample. Eligible veterans will be sent a recruitment letter with a postage paid return postcard asking them to indicate whether they have a non-VA provider or have ever used My HealtheVet for sharing health information with providers. When contacted, the research assistant will confirm inclusion criteria and request the date of the next scheduled VA-provider and

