non-VA provider appointment. Only those with upcoming visits with both providers in the next 6 months will be recruited. In our current work, we were able to use comparable methods to find veterans who had non-VA providers and we expect similar success in this study. To complete the study procedures, participants will be required to have access to a computer with internet, phone, and printer. At the time of enrollment, veterans will also be asked to complete a release of information so we may communicate with their non-VA provider and obtain a copy of their recent visit note, problem list, and medication list.

This pilot will be a randomized controlled trial comparing the CC intervention to usual care. This will allow for more conclusive determination of the impact of the intervention. In addition, results from this pilot can be compared to Dr.[name]'s pilot study examining unidirectional sharing of health information from the VA to non-VA providers only, to determine whether there was any additional benefit to bi-directional information sharing, the inclusion of the Co-Management Toolkit, and discussion of provider roles.

The study statistician will develop a computer program to implement randomization grouped in blocks to ensure equal distribution in study arms by age, gender, and race. The study coordinator will maintain randomization assignments in sealed envelopes to ensure that randomization and recruitment of specific patients is not influenced by future assignments. Veterans and providers in the usual care condition will complete all the same assessments, but will otherwise receive no aspects of the intervention.

Intervention Arm:

Veteran Intake Interview: In the intake interview, conducted by phone, veterans will be asked to confirm their medical conditions and list all their providers, including pharmacies, provide provider contact information, and to specify what roles and responsibilities are held by these providers (initial draft of form can be found in Appendix C). Veterans will also provide the dates of upcoming VA and non-VA provider visits. The results of the interview will be summarized. Veterans will also complete the Patient Perceptions of Integrated Care Survey(18, 19) with instructions to rate their experience in the past year. This initial assessment will serve as the baseline measure for patients' perceptions of CC.

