Within My HealtheVet, a veteran can attach a file to their secure message and send that file to their VA health care team. If deemed clinically relevant, the VA health care team can then save that secure message in CPRS as a note and also save the file attachment In VistA Imaging. Phase 1 of this functionality was released in March 2014 and Phase 2 is scheduled for the 12.9 release of My HealtheVet in June 2014. Phase 2 will allow for a total of 4 file attachments per message with a maximum cumulative size of 6MB. The content included in the materials sent to the VA through secure messaging will be determined during the initial intake interview and will be shaped by perceived functions of health care team members. However, in general, patients will be asked to include a copy of their medication list, problem list, and most recent labs and most recent visit note.

We will instruct veterans to secure message non-VA health information to their PACT nurse care manager. The nurse care manager will then save the relevant information in CPRS and also notify other VA treatment team members, such as specialty care providers, of receipt of this information. We have discussed this process with ICVAHCS PACT leadership and they agree to promote this workflow.

Provider Visit: Veterans in both conditions will be followed in the study until they have had one VA and one non-VA provider visit. Those in the intervention arm will receive a reminder call one week prior to these visits

instructing them to bring hard copies of their list of providers and either their CCD from the VA, and informational aspects of the co-management toolkit (for non-VA providers) or most recent information from their non-VA care (for VA providers). Veterans will be asked to share this information with their providers and discuss whether or not the provider was aware of the other care and whether or not the provider concurs with the attributed roles. If discrepancies in expectations exist, the veteran will notify the PACT nurse care manager and work with the relevant stakeholders to start to clarify roles. Data about such discrepancies will be described in detail as part of the qualitative study of clarification of roles.

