Veterans in both study conditions will also be provided a postage paid envelope and brief evaluation forms to be completed by their providers and by the veteran. The patient post-visit questionnaire will include the Patient Perceptions of Integrated Care Survey. The provider forms include confirmation of receipt of information, its impact on care, provider satisfaction (Appendix E), and Gittell's Seven Item Measure of Relational Coordination designed for providers(20). (Appendix F) Gittell's 7-item measure of Relational Coordination assesses providers' perceptions of the frequency, timeliness, accuracy and problem-solving nature of communication, as well as relationships of shared goals, knowledge, and mutual respect. To facilitate participation, a waiver of signature of consent will be obtained from the IRB for providers.

The provider post-visit questionnaire will be comparable to the one currently used in the HSR&D study but additional questions will be added pertaining to the designation of provider roles, knowledge of and acceptability of CC agreements, and the usefulness of the Co-management Toolkit for non-VA provider questionnaires. The questionnaire will also include a section where the physician can indicate if he or she would be willing to complete a 15 minute audio-recorded qualitative interview about the medical visit. Although the proposed methods make some immediate demands on non-VA providers, response rate for the brief evaluation forms was high and 5 out of 21 providers agreed to be interviewed. Non-VA providers will also receive a small financial incentive for participation.

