Post Medical Visit Provider and Veteran Interviews: Providers and veterans who agree will be interviewed briefly by phone about their experience during the medical visit with a focus on CC. Willing veterans will be interviewed regardless of whether their provider does an interview. We will plan to conduct these interviews within one week of the scheduled appointment. If the non-VA provider agrees to complete a qualitative interview, a separate consent letter will be provided at that time prior to data collection detailing the information to be obtained. Again, a waiver of signature of consent will be utilized with clear instructions that by completing the audio recorded interview that he/she is providing consent to participate. The interview will address two main issues: the impact of the information exchange on the visit, and the acceptability and optimal design of a co-management care coordination agreement.

Outcome Assessments and Quantitative Analysis: The main outcomes of this study and when they will be collected are presented in Table 2. Though ordered in the table, we will not dictate what order the VA and non-VA provider appointments must occur – though this order will be noted in data collection. As this is a pilot study, we are conducting analyses to determine an estimate of effect size and expected variability to be used in a later power calculation for a larger experimental or quasi-experimental study.

Table 2: Study Assessments

Outcome			
Patient Perceptions of Integrated Care	Baseline	Post VA Visit	Post Non-VA Visit
Provider Relational Coordination Survey		Post VA Visit	Post Non-VA Visit
Medication Concordance- From Chart		Post VA Visit	Non-VA Visit
Medical Duplication- From Chart		Post VA Visit	Post Non-VA Visit

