Hypothesis 3: Medication concordance will be higher for patients in the intervention arm than usual care. Medication concordance for each of the two medical visits will be calculated by making two lists, the current VA medication list and the current non-VA medication list. The former will be taken from CPRS while the latter will be taken from the non-VA provider visit most proximal temporally to the VA visit. We will obtain both the visit note and the medication list from the providers' visits. If the note does not indicate any medication change and there is none indicated on the form we ask the provider to complete, the provider's medication list will be designated the final medication list documented for that visit. If there is an indication of a specific medication change, either in the note, or in the form we request providers to complete, the discrepancy pertaining to this change will not be counted as an "unreconciled" medication.

Our metric for concordance of medication lists will be based on reviewing both the VA and non-VA medication lists and determining the total number of distinct medications. A distinct medication is defined by 1) the type of medication and 2) the daily dose. The final calculation of appropriate medication concordance will be calculated as the total number of distinct medications included on both lists divided by the total number of distinct medications. This way, the possible range is from 0 to 1 with 1 indicating perfect concordance of medication lists. The metric will range from 0 to 1, but we expect agreement between the two medication lists to yield estimates ranging between 0.50 and 0.90 based on prior research in medication appropriateness(10, 21). We will first examine the distribution of medication concordance to determine the appropriate statistical test. If the distribution is highly skewed, we may categorize the variable into two or more categories (e.g., <10%, 50%, or >=80% agreement) and evaluate differences between patients in the intervention and usual care groups using a Chi-square test. Alternatively, medication concordance may be treated as a continuous variable and evaluated using the t-test or Wilcoxon rank sum.

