Hypothesis 4: Medical duplication will be lower for patients in the intervention arm than usual care. Prior research has quantified therapeutic and laboratory duplication, yet these are clearly difficult constructs to operationalize(10, 21-23). Therapeutic duplication will be defined as concurrent use of more than one medication from the same therapeutic class, based on modified VA classes, according to the method published by Fitzgerald et al. (24) and more recently adapted by Chrischilles et al.(10). For laboratory duplication, we will identify all orders for labs occurring within the 6 months prior to the non-VA provider visit. For sensitivity analysis, we will compare different intervals, e.g., 14 days, 30 days, 60 days. Since there are multiple indications for laboratory referrals, we will collect temporally associated diagnoses. Each patient will be assigned a dichotomous indicator for whether they received therapeutic duplication and/or laboratory duplication during their non-VA provider visit.

To validate these metrics, all instances of identified duplication plus a random sample of visits where no apparent duplication occurred will be reviewed by [name], a clinical pharmacist, and [name], head of the ICVAHCS pathology department. Both are current collaborators on [name] HSR&D and ORH study. Drs. [name] and [name] will be blind to whether or not the visit met criteria for treatment or diagnostic redundancy and they will also be blind to the treatment arm of the patient whose visit is being reviewed. Their clinical assessment of presence of duplication will be used to validate the metric. If agreement is poor between these two raters and the criteria described above (Kappa > 0.80), the investigative team will meet to determine the source of the discrepancy and how to remedy it. Each patient will be assigned a dichotomous indicator for whether they received either therapeutic or laboratory duplication during their non-VA provider visit. Differences in the occurrence of medical duplication between usual care and intervention groups will be examined using the Chi-square test.

REFERENCES

1. 2011 Survey of Veteran Enrollees' Health and Reliance upon VA. . 2011.

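### Masking is not planned for scoring medication concordance (Hypothesis 3) and is not secured for validating and revising the duplication metric (Hypothesis 4)

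*Combined protocol and SAP*

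**What the plan says.** **Hypothesis 3.** Concordance is the number of distinct drugs on both lists divided by the total number of distinct drugs. A mismatch is not counted as unreconciled under this condition: "If there is an indication of a specific medication change, either in the note, or in the form we request providers to complete". The section names no coder and mentions no masking.

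**Provider forms (Provider Visit).** "The provider forms include confirmation of receipt of information, its impact on care, provider satisfaction". The non-VA form also asks how useful the Co-management Toolkit was. Usual-care providers complete the same assessments, but neither they nor their patients receive any part of the intervention.

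**Secure messaging (Intervention Arm).** If the VA team judges the material clinically relevant, it can "save that secure message in CPRS as a note and also save the file attachment".

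**Hypothesis 4.** A pharmacist and a pathologist review the flagged visits and a random sample of unflagged ones. They do not know the metric result, and "they will also be blind to the treatment arm of the patient whose visit is being reviewed". Their assessment validates the metric. If agreement is poor, "the investigative team will meet to determine the source of the discrepancy and how to remedy it". The printed condition for poor agreement is a kappa above 0.80.

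**Purpose (Outcome Assessments and Quantitative Analysis).** "we are conducting analyses to determine an estimate of effect size and expected variability", for use in a later power calculation.

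**The concern.** Patients and providers know what they received, and they report the outcomes of Hypotheses 1 and 2 themselves. The two chart outcomes offer the best chance of assessment without knowledge of arm. That chance is lost if the person deciding which mismatches to excuse reads answers about shared information and the Toolkit while deciding. It is also lost if the duplication definition can be changed by people who may know the arms.

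What is at stake is the effect-size estimate that the pilot exists to supply. A small drift in scoring towards the hypothesis would pass directly into the planning of the larger study.

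**Working it through.** **1. Can the Hypothesis 3 coder infer the arm?** The scoring rule sends the coder to the provider form. The form asks about receipt of information and, for non-VA providers, the Toolkit. Only intervention patients are trained and reminded to bring such information, and only their non-VA providers are sent the Toolkit. The blank form is the same in both arms, but the completed answers will tend to differ. Nothing in the plan separates the medication-change item from the rest.

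**2. How much discretion does the coder have?** The formula has no term for an excused mismatch. The coder could drop the drug from the denominator or count it as agreement. The plan does not say which.

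**3. What protects Hypothesis 4?** Blinding is stated, but the material given to the reviewers is not described. Intervention material may be stored in CPRS, so an unredacted chart could disclose the arm. The analysed outcome is a dichotomous indicator based on drug class and laboratory-order windows, and the plan does not say that the reviewers' judgement replaces it. Failed blinding would therefore act mainly through the revision step. For that step no masking, timing or limit is stated, and the printed trigger describes good rather than poor agreement.

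**4. Size, for illustration.** The plan gives no SD, alpha or power, so there is no figure of its own to reproduce.

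Inputs from the plan:
- Total sample: "Sixty dual use veterans who have a non-VA provider".
- Allocation is blocked "to ensure equal distribution in study arms by age, gender, and race", read here as 30 per arm.
- Expected concordance is 0.50 to 0.90.

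Assumptions not in the plan:
- There are 10 distinct drugs per patient, 7 of them matched.
- The expected range spans about 4 SDs, so SD = (0.90 − 0.50)/4 = 0.10.
- Data are complete, and extra excusals occur in the intervention arm only.

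Shift per affected patient:
- Excused drug dropped from the denominator: 7/9 − 7/10 = 0.778 − 0.700 = 0.078.
- Excused drug counted as agreement: 8/10 − 7/10 = 0.100.

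Standard error of the arm difference = SD × √(2/30) = 0.258 SD, or 0.026 at SD 0.10.

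The last column is the chance of a significant result favouring the intervention when there is no true effect. It is Φ(shift/SE − 1.96), with two-sided alpha 0.05 assumed, so its value without bias is 0.025.

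| Patients with one extra excusal | Handling | Shift in arm difference | In SDs (SD 0.10) | False favourable result, SD 0.10 / SD 0.20 |
|---|---|---|---|---|
| 10% | dropped | 0.008 | 0.08 | 0.049 / 0.035 |
| 25% | dropped | 0.019 | 0.19 | 0.114 / 0.057 |
| 10% | agreement | 0.010 | 0.10 | 0.058 / 0.039 |
| 25% | agreement | 0.025 | 0.25 | 0.161 / 0.070 |

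For Hypothesis 4, each intervention patient reclassified from duplication to none moves the arm difference by 1/30 = 3.3 percentage points.

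**The case against.** A reader might infer that the Hypothesis 4 reviewers see intervention documents, that the investigative team knows the arms, and that any revision comes after the outcomes are in. The documents support none of these. The reviewers are stated to be blind, and their review material is not described. Secure messages are saved only if judged relevant. Assignments are held by the study coordinator in sealed envelopes, and neither the team's masking nor the timing of its meeting is given. Nor do the reviewers set the outcome. What can be said is that blinding is promised without a procedure and that the revision step has no stated safeguard.

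It would also be too strong to say that the form reveals the arm. It is common to both arms, a usual-care veteran may bring information too, and the form's layout is not available here. The rule asks for a specific medication change, which limits the coder's freedom. Likely disclosure to a coder with no planned masking still stands.

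Two further objections stand as limits. The illustrative shifts are smaller than one standard error, and nothing shows that drift occurs. And if providers themselves record more changes in the intervention arm, a masked coder would not correct that.

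Pilot status does not remove the point, because the estimated effect size is the pilot's intended product.

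**Conclusion.** The point holds in limited form. For Hypothesis 3, masking is not planned, and the scoring rule relies on a form whose answers will probably show the arm. For Hypothesis 4, blinding is stated but not secured, and the metric can be revised without a stated mask, time or lock, on a trigger that reads the wrong way round.

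The possible bias is modest. With an excused drug dropped from the denominator it is 0.08 to 0.19 SD, if one extra mismatch is excused in 10% to 25% of intervention patients. That rests on the assumed list of 10 drugs with 7 matched, the assumed SD of 0.10, and excusal frequencies for which the documents give no evidence. It is enough to distort a planning estimate, and it does not show that the results would be biased. The change is worth making because it is cheap.

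**What to change.** - **Hypothesis 3.** Existing staff transcribe only the medication-change item from the provider form. They pass it, with the two medication lists and the visit note, under study ID to a coder who does not have the arm. State how an excused mismatch enters the formula.
- **Packets for Hypotheses 3 and 4.** Leave out secure-message notes and attachments, the CCD, the Toolkit, the role list and the provider letter. The non-VA visit note and medication list are obtained by release of information in any case, so those sources are not lost.
- **Revision of the duplication metric.** Correct the kappa condition so that it describes poor agreement. Decide any change masked to arm, apply it to all patients, lock it before arm codes are merged, and report results under the original definition alongside.

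**Cost.** There are at most 60 × 2 = 120 visit packets. At an assumed 5 to 10 minutes each, that is 10 to 20 hours of existing-staff time, plus protocol wording. No new assessor is needed. Masking may remain incomplete where a visit note itself mentions the intervention, and differential recording of changes by providers is not addressed.

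### The medication-concordance exemption is not limited to changes made at the later visit and has no place in the formula, so it can excuse the sharing failure that the outcome is meant to detect

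*Combined protocol and SAP*

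**What the plan says.** Hypothesis 3 compares a current VA list, taken from CPRS, with the non-VA list from the non-VA visit closest in time to the VA visit. Concordance is to be calculated for each of the two visits.

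The exemption is triggered as follows: "If there is an indication of a specific medication change, either in the note, or in the form we request providers to complete". The consequence is that "the discrepancy pertaining to this change will not be counted as an 'unreconciled' medication". Nothing is said about whether the change belongs to the earlier or the later visit, how much time has passed, or whether the other system was told.

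The next paragraph defines the score as "the total number of distinct medications included on both lists divided by the total number of distinct medications". On the unit counted: "A distinct medication is defined by 1) the type of medication and 2) the daily dose". No count of unreconciled items appears in that definition.

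Three other places bear on this:

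- Aim 2 names concordance of medication lists as an indicator of the impact of health information sharing.
- The text introducing Table 2 leaves the order of the VA and non-VA visits open but says the order will be recorded.
- Masking of chart review is stated under Hypothesis 4, for the duplication reviewers only: "they will also be blind to the treatment arm of the patient whose visit is being reviewed". No masking is stated for concordance coding.

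**The concern.** A discrepancy that follows a documented change can mean two different things. If the change was made at the later of the two visits, the other system has had no chance to record it, and excusing it is reasonable. If it was made at the earlier visit and is still absent from the other list at the later one, the information did not travel. The intervention aims to prevent that second case. A rule that excuses both cases removes part of the signal from the outcome.

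The exemption also has no defined route into the score. An analyst could ignore exempted items, drop them or count them as agreeing, and these give different values for the same patient. The pilot is meant to supply an effect size and a variability estimate for a later power calculation, so an ill-defined or diluted score would carry over into the design of the next study.

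**Working it through.** The plan gives no power, standard deviation or effect size for this outcome, so there is no planning figure to reproduce. Its only numeric expectation is that "we expect agreement between the two medication lists to yield estimates ranging between 0.50 and 0.90".

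**1. One patient, three readings.** Let N be the number of distinct drugs, s the number on both lists and c the number of exempted discrepancies. N = 10 is an assumption; s = 5, 7 and 9 span the plan's expected range.

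- Formula as written: s/N
- Exempted items dropped: s/(N − c)
- Exempted items counted as concordant: (s + c)/N

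| s of 10 | c | As written | Dropped | Counted |
|---|---|---|---|---|
| 5 | 2 | 0.50 | 5/8 = 0.625 | 7/10 = 0.70 |
| 7 | 1 | 0.70 | 7/9 = 0.778 | 8/10 = 0.80 |
| 7 | 2 | 0.70 | 7/8 = 0.875 | 9/10 = 0.90 |
| 9 | 1 | 0.90 | 9/9 = 1.00 | 10/10 = 1.00 |

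With 7 of 10 shared, a single exemption reaches the plan's example category of at least 80% agreement if counted as concordant, and falls just short of it if dropped.

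Because daily dose is part of the definition, one dose change that is not passed on creates two non-shared items. The plan does not say whether its exemption covers one or both.

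**2. Effect on a real benefit.** Take 10 drugs, 7 shared, with one of the other three newly added at the earlier visit.

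- Intervention patient, change passed on: 8/10 = 0.80.
- Usual-care patient, change not passed on: 7/10 = 0.70. True difference: 0.10.
- Usual-care patient after exemption: 0.778 (dropped) or 0.80 (counted).
- Remaining difference: 0.80 − 0.778 = 0.02, or 0.80 − 0.80 = 0.

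This dilution needs no difference between arms in how changes are documented.

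**3. Unequal exemption with no true difference.** From the documents: "Sixty dual use veterans who have a non-VA provider", with blocked randomization "to ensure equal distribution in study arms by age, gender, and race", taken here as 30 per arm. Assumed: 10 drugs each, true agreement distributed Beta(7,3) with mean 0.70 in both arms, a two-sided t-test at 0.05, and 4,000 simulated trials. The share of discrepancies exempted is also assumed, since the documents give none. Differences are intervention minus usual care.

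| Share exempted: usual care / intervention | Difference: dropped / counted | Rejection rate: dropped / counted |
|---|---|---|
| 20% / 20% | 0.000 / 0.000 | 4.7% / 4.6% |
| 20% / 30% | +0.022 / +0.029 | 7.6% / 10.4% |
| 10% / 30% | +0.043 / +0.059 | 14.6% / 26.0% |
| 30% / 10% | −0.044 / −0.060 | 14.5% / 26.4% |

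As a check on the counted figures, the expected difference is mean discordance times the difference in shares: 0.30 × (0.30 − 0.10) = 0.06. With the formula as written and no exemption, the difference is about 0.00 and rejection is 4.5% to 5.2% in every scenario run.

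**The case against.** Three points on the other side deserve weight.

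**The formula is unaffected if taken literally.** It contains no exemption term, so an analyst who follows it exactly gets an undistorted ratio. That is correct, but the exemption sentence then has no function. The two paragraphs do not fit together, and the plan must say which governs.

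**The rule may be meant visit by visit.** Concordance is calculated for each visit, and the preceding sentence fixes the final list for that visit. A reader could take the note and the form to be those of the visit being scored, which would confine the exemption to changes just made. The wording allows this reading but does not require it.

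**Bias in favour of the intervention is not shown.** A reader might infer that intervention providers, given outside information and asked about its impact, will document more changes and so earn more exemptions. The documents do not support that inference:

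- The same assessments and provider forms go to both arms.
- More documented changes need not mean more exempted discrepancies, because a change made in response to outside information may bring the lists into line and leave nothing to excuse.
- Changes that are not passed on should, if the intervention works, be commoner in usual care. Excusing them would then shelter usual care and pull the comparison towards no difference.

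This objection stands. Unequal exemption remains possible, since concordance coding is not stated to be masked, but its direction cannot be read from the plan. Nor is there a good case for ignoring the provider form as a source of changes: it is a planned source of true changes, and providers could equally write more in their notes.

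**Conclusion.** The point holds as a defect in the definition of the outcome. As worded, the exemption covers changes made at either visit and can excuse a failure to pass on an earlier-visit change. How an exempted item enters the score is undefined.

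In the worked case, one exemption raises a score of 0.70 by 0.078 or 0.10, and a true benefit of 0.10 falls to 0.02 or 0. These figures assume 10 drugs, one added drug that was not passed on, and an analyst who applies the exemption by dropping the item or counting it as concordant.

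A spurious difference between arms is a conditional risk only. It requires unequal exemption shares, it can favour either arm, and the simulated sizes depend on shares that the documents do not give. With equal shares and no true difference, the rejection rate stays near 5%. The simulation should not be cited as evidence that the plan favours the intervention.

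**What to change.** Amend the wording of Hypothesis 3 as follows:

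1. Using the recorded visit order, exempt a discrepancy only if it comes from a change made at the later of the two paired visits. Count an earlier-visit change that is missing from the other list as discordant.
2. Remove exempted items from both numerator and denominator, and state that a dose change exempts both of the entries it creates.
3. Keep both the visit note and the provider form as sources of changes.
4. Code exemptions masked to arm where feasible. Forms that confirm receipt of outside information may reveal the arm, so full masking may not be possible.
5. Report concordance with no exemptions as a sensitivity analysis, and the number of exempted items by arm.

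The cost is small. Visit order, notes, lists and forms are already to be collected, so the work is wording, masking of list pairs and one further tabulation. The downside is that some earlier-visit changes will count as discordant even when the visits were close together, so scores will be slightly lower in both arms.
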